5 TABLE OF EVENTS

		E				Induc	tion Pe	riod			Maintena nce Period	At 3 cycles (84 days after		Follo	ow-up	
PROCEDURE ^a	Screening Period	Every Cycle Day 1 Induction & Maintenance Periods (± 3 days)	C	ycle 1	l	Cycles 2 & 3	Cycles 3, 5, 7, 9 & 11	Cycles 5 & 9	Cycle 7	Cycle 10	Cycles 13, 15, 17, 19, 21, 23, 25, 27 & 29	At 6 cycles (168 days after C1D1)(±2 weeks)		If no PD then follow the CT		Ŧ
	Days -28 to -1	Up to PD for Arm A Or up to 30 cycles for Arm B	Day 1 (± 3 days)	Day 8 & 15 (± 1 day)	Day 22	Day 15 (± 1 day)	Day 1	Day 1 (± 3 days)	Day 1 (± 3 days)	Day 1 (± 3 days)	Day 1 (± 3 days)	Every 6 cycles (168 days) (±2 weeks) up to 5 years then Annually (± 3 weeks) ^b	At Treatment Discontinu ation/ Completio n	scan assessment schedule ^b		
Informed Consent	Х	-	-	-	-	-	-	-	-	-	-	-	-	-	-	
Inclusion/Exclusion Criteria	X	-	-	-	-	-	-	-	-	-	-	-	-	-	-	-
Demographic Data	Х	-	-	-	-	-	-	-	-	-	-	-	-	-	-	-
Lymphoma and Complete Medical History	х	-	-	-	-	-	-	-	-	-	-	-	-	-	-	-
Central Nervous System Lymphoma Evaluation	х	-	-	-	-	-	-	-	-	-	-	-	-	-	-	-
Creatinine Clearance (Cockcroft-Gault Estimation)	х	-	-	-	-	-	-	-	-	-	-	-	-	-	-	-
12-Lead Electrocardiogram	Х	-	-	-	-	-	-	-	-	-	-	-	-	-	-	-
HBV Screening ^c	Х	-	-	-	-	-	-	-	-	-	-	-	-	-	-	-

		E				Induc	tion Pe	riod			Maintena nce Period	At 3 cycles (84 days after		Follo	ow-up	
PROCEDURE ^a	Screening Period	Cycle Day 1 Induction & Maintenance Periods (± 3 days)		Cycle 1	L	Cycles 2 & 3	Cycles 3, 5, 7, 9 & 11	Cycles 5 & 9	Cycle 7	Cycle 10	Cycles 13, 15, 17, 19, 21, 23, 25, 27 & 29	At 6 cycles (168 days after C1D1)(±2 weeks)		If no PD then follow the CT		Ŧ
	Days -28 to -1	Up to PD for Arm A Or up to 30 cycles for Arm B	Day 1 (± 3 days)	Day 8 & 15 (± 1 day)	Day 22	Day 15 (± 1 day)	Day 1	Day 1 (± 3 days)	Day 1 (± 3 days)	Day 1 (± 3 days)	Day 1 (± 3 days)	Every 6 cycles (168 days) (±2 weeks) up to 5 years then Annually (± 3 weeks) ^b	At Treatment Discontinu ation/ Completio n	scan assessment schedule ^b		
Eastern Cooperative Oncology Group (ECOG) Performance Status	X	-	-	-	_	-	-	-	-	-	-	-	X	-	-	-
B Symptoms	Х	-	-	-	-	-	-	-	-	-	-	-	Х	-	-	-
Vitals Signs	X	X	-	-	-	-	-	-	-	-	-	-	X	-	-	-
Hematology Laboratory Tests ^g	X	Х	-	x	-	X	-	-	-	-	-	-	Х	-	-	-
Serum Chemistry Laboratory Tests ^g	X	Х	-	x	-	X	-	-	-	-	-	-	X	-	-	-
Thyroid Stimulating Hormone ^{g,n} (TSH)	X	-	-	-	-	-	-	-	-	-	-	-	х	-	-	-
Tumor Flare and Tumor Lysis Assessments ^h	-	-	X	x	-	-	-	-	-	-	-	-	-	-	-	-

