10.2 Study Population Definitions

The following three populations, defined as below, will be used in the analysis.

Intent-to-treat (ITT) population: The ITT population is defined as all subjects who are randomized and have received at least one dose of maintenance therapy.

The ITT population will be used for the primary efficacy analysis. Subjects will be analyzed according to the treatment arm to which they are initially assigned.

Modified Intent-to-treat (mITT) population: The mITT population is defined as all subjects who satisfy the following conditions:

- 1) are randomized
- 2) have received at least one dose of maintenance therapy
- 3) have confirmed diagnosis of relapsed/refractory FL grades 1-3b, transformed FL, MZL, or MCL
- 4) have SD, PR or CR/CRu after completing induction therapy
- 5) have at least one tumor assessment for efficacy after beginning of maintenance therapy

The efficacy analysis will also be performed on the mITT population as supportive evidence and/or sensitivity analysis. Subjects will be analyzed according to the treatment arm to which they are initially assigned.

Safety population: The safety population is defined as all subjects who have received at least one dose of study drug, including induction therapy. The safety population will be used for all safety analyses. For safety analysis of the maintenance period, subjects will be analyzed according to the treatment that they actually received.

Induction Efficacy Population: The Induction Efficacy Population is defined as all subjects who meet all of the criteria for eligibility into the study.

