10.6 Efficacy Analysis

All efficacy analyses will be performed on the ITT population. Efficacy analyses will also be performed on the mITT population as supportive evidence and to assess robustness of efficacy findings. Subjects will be analyzed according to randomized treatment group.

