10.6.1 Primary Efficacy Endpoint

Progression-free Survival

The primary efficacy endpoint for the study is PFS, which is defined as the time from the first dose date of maintenance therapy to objective disease progression or death from any cause, whichever occurs first. The PFS events will be determined using a modification of the IWG 1999 criteria (Cheson, 1999).

Subjects who did not experience disease progression and who did not die before the clinical data cut-off date will be censored at the time of the last visit with adequate response assessment when the subjects were known not to have progressed. Subjects who received new anticancer therapy without objective disease progression will be censored at the date of the last radiological assessment prior to the new anticancer therapy.

The primary efficacy endpoint will be compared between the two treatment arms when 114 PFS events that happen after the first dose date of maintenance therapy are observed.

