10.8 Interim Analysis

A formal interim analysis for futility only is planned to examine the overall response rate to induction therapy, which is defined as the proportion of subjects whose response at the end of induction period is at least PR (including CR, CRu and PR). It will be conducted with the first 50 efficacy evaluable subjects by the end of the Induction Period. Efficacy evaluable subjects are defined as subjects who have had the scheduled response assessment at 12 months, or progressed or died before the end of the Induction Treatment Period. If the lower limit of the 95% confidence interval for overall response rate during the induction period in these 50 subjects is less than 30% then the trial might be stopped for futility.

Since this interim analysis is only to evaluate the induction therapy, it has no impact on the number of events we need for the maintenance period, sample size, or alpha.

Considering the current PFS event rate and estimated timing of final analysis, one nonbinding interim analysis for patients in the maintenance phase is planned at 50% of information (95 PFS events) for both superiority and futility. The date of occurrence of the 95th PFS event will be used as data cut-off date for the analysis. This interim analysis will be conducted by an external independent statistician, while the study team will remain blinded.

The study may be stopped early for futility if the observed hazard ratio (HR) is > 1.154, based on Gamma (-8) family (Hwang, Shih, and DeCani, 1990), ie, in favor of the control arm, and/or if recommended by the DMC based on the safety profile of this combination regimen. The stopping boundary for superiority based on O'Brien Fleming Analog (Lan & DeMets, 1983) is hazard ratio ≤ 0.546 , if the observed HR cross the superiority boundary in favor of the proposed treatment, the trial may stop and claim the superiority. To ensure the overall 1-sided type 1 error remains at 0.025, an appropriate amount of alpha will be spent for the interim analysis.

The DMC will review the efficacy and safety data from these analyses and communicate recommendations to the sponsor who may use the recommendations in a risk/benefit analysis.

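### The mITT set used to check robustness drops any subject who dies before a first maintenance tumour assessment, although that death is a PFS and OS event in the ITT set

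*Combined protocol and SAP*

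**What the plan says.** Section 10.2 defines the primary set by randomisation and dosing only: "The ITT population is defined as all subjects who are randomized and have received at least one dose of maintenance therapy". The mITT set keeps both conditions and adds three more: a confirmed diagnosis, stable disease or better after induction, and, as criterion 5, that subjects "have at least one tumor assessment for efficacy after beginning of maintenance therapy". No exception is stated for subjects who die first.

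The role of the set is given twice. Section 10.2 says "The efficacy analysis will also be performed on the mITT population as supportive evidence and/or sensitivity analysis", and Section 10.6 says "Efficacy analyses will also be performed on the mITT population as supportive evidence and to assess robustness of efficacy findings". Neither statement limits the set to PFS. The only other sensitivity analysis that Section 10.6.4 names for time-to-event endpoints is the unstratified log-rank test, so the mITT is the only check that uses a different population.

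Section 10.6.1 defines PFS as "the time from the first dose date of maintenance therapy to objective disease progression or death from any cause, whichever occurs first". A subject with no event "will be censored at the time of the last visit with adequate response assessment when the subjects were known not to have progressed". Section 10.6.2 runs OS from the same start to death from any cause, and defines ORR, CRR and IOR as proportions of subjects. Table 1 and Section 6.3 place scans at 84 and 168 days from C1D1, then every 168 days, each with a two-week window, for five years.

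**The concern.** Criterion 5 depends on something that happens after randomisation and after maintenance has started. A subject who dies before any maintenance assessment has met the primary endpoint, yet fails the criterion because of that death. The set is meant to test whether the efficacy result is robust, but it removes one kind of endpoint event by definition. It therefore cannot test robustness to those events.

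The same rule reaches other endpoints. For OS a scan has no bearing on the outcome, yet an unscanned early death is still removed. For ORR, CRR and IOR, subjects with no maintenance assessment leave the denominator, which raises the proportion if they would otherwise count as non-responders.

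At stake is how the supportive analysis should be read. The primary result is not affected.

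**Working it through.** **1. The plan's own figures.** The assumed hazard ratio is not legible, but Section 10.3 says that 0.533 is 20% better, so it is 0.533/0.8 = 0.666. Schoenfeld's formula with 1:1 allocation, one-sided 0.025 and 80% power gives 4(1.960 + 0.842)²/(ln 0.666)² = 191 events, as stated. Power at 114 events is Φ(√114/2 × |ln HR| − 1.96). This gives 58.2% at 0.666 (57.9% stated) and 91.9% at 0.533 (92% stated). None of these figures is in dispute.

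**2. The unscanned interval.** Twelve induction cycles last 12 × 28 = 336 days, which is a scan date (2 × 168). The next scan is due 168 days later. Without cycle delays, the first scheduled maintenance scan comes about 24 weeks into maintenance.

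**3. Who is treated differently.**

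| Dosed subject | ITT, PFS | mITT |
|---|---|---|
| Dies with no maintenance assessment | Event | Removed |
| Progresses early | Event | Kept: Section 6.3 requires a CT even when progression shows elsewhere first |
| Stops treatment for toxicity | Followed on the same scan schedule (Sections 4.1.4 and 6.3) | Kept once scanned |
| Withdraws, is lost, or starts new therapy without progression, with no maintenance assessment | Censored at about day 1 | Removed |

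The last row carries almost no PFS information, so its removal hardly moves the hazard ratio. The first row is the one that matters for PFS. An unscheduled assessment before death keeps the subject in, so not every early death is lost.

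**4. Numbers affected.** Section 10.3 gives 5% annual dropout and about 314 randomised. Over 154 to 182 days, 1 − 0.95^(days/365.25) is 2.1% to 2.5%, or about 7 to 8 subjects. At 168 days it is 2.3%. If all of these were unscanned non-responders, removing them would multiply a response proportion by 1/(1 − 0.023) = 1.024.

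No early-death rate is given, so I assume 1% to 5% of 314. If 3, 6, 9 or 15 of the 114 events were unscanned early deaths, the mITT would hold 111, 108, 105 or 99 events. Power of that supportive analysis at 0.666 would fall from 58.2% to 57.1%, 56.0%, 54.8% or 52.4%.

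**5. Hazard ratio by event counts.** With equal arms, approximate the hazard ratio by the ratio of events. At 0.666 the 114 events split 45.6 in Arm A and 68.4 in Arm B.
- Remove 3 from A and 0 from B: 42.6/68.4 = 0.622
- Remove 3 from each: 42.6/65.4 = 0.651
- Remove 0 from A and 3 from B: 45.6/65.4 = 0.697

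**6. Simulation.** There were 157 subjects per arm, the cut was at 114 ITT events, and each scenario had 1,500 replicates. Assumptions: control median 60 months, progression first detectable at the first maintenance scan, early deaths uniform over that interval and all unscanned. Rejection uses 1.96, with no adjustment for the interim analysis.

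| Progression HR | Early deaths, A / B | ITT HR (rejection) | mITT HR (rejection) |
|---|---|---|---|
| 0.667 | 1% / 1% | 0.675 (54%) | 0.667 (55%) |
| 0.667 | 3% / 3% | 0.689 (50%) | 0.666 (53%) |
| 0.667 | 3% / 1% | 0.722 (41%) | 0.665 (54%) |
| 0.667 | 5% / 1% | 0.777 (26%) | 0.668 (52%) |
| 0.667 | 1% / 3% | 0.638 (65%) | 0.661 (55%) |
| 1.0 | 5% / 1% | 1.113 (1%) | 0.996 (3%) |

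Across the five rows at 0.667, the ITT estimate ranges from 0.638 to 0.777 while the mITT estimate stays between 0.661 and 0.668. The mITT does not register the early deaths.

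**The case against.** The strongest reply is that nothing decisive rests on this set. It is supportive, evaluable-subject sets are common, and the primary ITT set keeps every such death among dosed subjects. That stands, and it limits the point to a cheap improvement.

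Four stronger readings are tempting, and the documents support none of them.

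- **The rule favours Arm A.** Arm A adds lenalidomide to rituximab. In the placebo-controlled lenalidomide maintenance trial in DLBCL summarised in Section 1.7, Grade 3 or 4 neutropenia was 56% against 22%. That makes an imbalance plausible. However, it concerns another lymphoma and is not an early-death rate. No such rates are given by arm, and the bias reverses if Arm B has more of these deaths.
- **Agreement between the two sets gives false reassurance.** If unscanned deaths are unbalanced, the two estimates separate (0.777 against 0.668 above), which exposes the problem. If the estimates agree, the exclusion mattered little.
- **The exclusion could carry the result across the significance boundary.** Before any interim alpha spending, the critical hazard ratio at 114 events is exp(−2 × 1.96/√114) = 0.693, and a supportive estimate could fall below it. But the plan bases no decision on the mITT, and Section 10.8 commits part of the alpha to the interim, so 0.693 is not the final boundary either.
- **Toxicity dropouts are lost.** Stopping treatment does not stop scanning, and subjects who leave unscanned add almost nothing to ITT PFS.

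A further objection is that without criterion 5 the mITT is nearly the ITT, because eligibility and randomisation already require the diagnosis and at least stable disease. That is correct, and it is the price of the change.

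**Conclusion.** The point holds in a limited form. Criterion 5 removes subjects who die before any maintenance assessment from a set described as a test of robustness, although each is a PFS and OS event in the primary set. It also removes unassessed subjects from the mITT denominators for ORR, CRR and IOR.

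The PFS bias can go either way. Under the assumed rates, the mITT hazard ratio was lower than the ITT one by 0.057 at 3% against 1% (0.722 to 0.665) and higher by 0.023 at 1% against 3% (0.638 to 0.661). With equal rates of 3% it was lower by 0.023 (0.689 to 0.666). These sizes rest on assumed early-death rates, an assumed control median and no unscheduled scans before death, so they are illustrations and not estimates for this trial.

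The primary ITT analysis, alpha and the 114-event trigger do not change. Subjects randomised but never dosed are absent from both sets, which is a separate question.

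**What to change.** Delete criterion 5 from the mITT definition in Section 10.2 and keep criteria 1 to 4. The dosing criterion must stay, because PFS starts at the first maintenance dose and an undosed subject has no start date. At minimum, state that a subject who dies before the first maintenance assessment remains in the mITT.

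Then specify the handling. Death before any maintenance assessment is an event. Other subjects with no maintenance assessment are censored at day 1 for PFS and counted as non-responders for ORR, CRR and IOR.

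The cost is one deleted line and a changed population flag, settled before the final analysis. It needs no new data, sample size or alpha. The downside is that the mITT moves closer to the ITT, differing only through diagnosis and end-of-induction response status, so it becomes a narrower check.

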10.4 Background and Demographic Characteristics

All subjects' age, height, weight, and baseline characteristics will be summarized using descriptive statistics, while gender, race, histology, and other categorical variables will be provided using frequency tabulations. Medical history data will be summarized using frequency tabulations by system organ class and preferred term.

10.5 Subject Disposition

Subject disposition (analysis population allocation, randomization status, discontinuation of treatment, primary reason for early treatment discontinuation, discontinuation of study, and primary reason for early study discontinuation) will be summarized using frequency and percentage for all enrolled subjects. A summary of subjects enrolled by site will be provided. Protocol deviations will be summarized using frequency tabulations.

10.6 Efficacy Analysis

All efficacy analyses will be performed on the ITT population. Efficacy analyses will also be performed on the mITT population as supportive evidence and to assess robustness of efficacy findings. Subjects will be analyzed according to randomized treatment group.

10.6.1 Primary Efficacy Endpoint

Progression-free Survival

The primary efficacy endpoint for the study is PFS, which is defined as the time from the first dose date of maintenance therapy to objective disease progression or death from any cause, whichever occurs first. The PFS events will be determined using a modification of the IWG 1999 criteria (Cheson, 1999).

Subjects who did not experience disease progression and who did not die before the clinical data cut-off date will be censored at the time of the last visit with adequate response assessment when the subjects were known not to have progressed. Subjects who received new anticancer therapy without objective disease progression will be censored at the date of the last radiological assessment prior to the new anticancer therapy.

The primary efficacy endpoint will be compared between the two treatment arms when 114 PFS events that happen after the first dose date of maintenance therapy are observed.

10.6.2 Secondary Efficacy Endpoint

Secondary efficacy endpoints will include OS, IOR, ORR, CRR, DOR, DOCR, TTNLT and TTHT.

Overall Survival

The OS is defined as the time between the first dose date of maintenance therapy and death from any cause. Subjects who complete the study and are still alive at the time of the clinical data cutoff date will be censored at the last visit date or the last contact date, whichever is later. Subjects who were lost to follow-up prior to the clinical data cut-off date will also be censored at the time of the last contact. Overall survival information will be collected for 5 years from the date of the last subject initiating induction therapy. The additional OS data may be analyzed as supplementary information. No formal hypothesis testing will be performed post the final primary endpoint analysis.

Improvement of Response

Improvement of response is defined as the proportion of subjects who have improved their tumor response during the maintenance phase, that is, the proportion of subjects who are converted from PR at the end of induction period to CR/CRu as best response, and subjects who are converted from SD at the end of induction period to PR or better as best response during the maintenance phase.

Overall Response Rate

Overall response will be analyzed in two aspects. The overall response rate at the end of 18 cycles of maintenance therapy is defined as the proportion of subjects with a response of at least PR (including CR, Cru, and PR) by the end of 18 cycles of maintenance therapy and prior to any treatment change.

In addition, best ORR, defined as the proportion of subjects with a best response of at least PR (including CR, CRu and PR) after the first dose date of maintenance therapy and prior to any treatment change, will also be presented.

Complete Response Rate

Complete response will also be analyzed in two aspects. The complete response rate at the end of 18 cycles of maintenance therapy is defined as the proportion of subjects with a response of at least CRu (including CR and CRu) by the end of 18 cycles of maintenance therapy and prior to any treatment change.

In addition, best CRR, defined as the proportion of subjects with a best response of at least CRu (including CR and CRu) after the first dose date of maintenance therapy and prior to any treatment change, will also be presented.

Duration of Response

Duration of response is defined only for subjects who have achieved PR or better after the first dose date of maintenance therapy and prior to any treatment change. It is calculated as the time from the initial response (at least PR) after the first dose date of maintenance therapy and prior to treatment change to documented disease progression or death.

Subjects who have not progressed or died at the time of the clinical data cutoff date will be censored at the last assessment showing no progression. Subjects who change treatment without evidence of disease progression will be censored at the last assessment showing no progression prior to treatment change.

Duration of Complete Response

Duration of complete response is defined only for subjects who have achieved CR/CRu after the first dose date of maintenance therapy and prior to any treatment change. It is calculated as the

time from the initial response (at least CRu) after the first dose date of maintenance therapy and prior to treatment change to documented disease progression or death.

Subjects who have not progressed or died at the time of the clinical data cutoff date will be censored at the last assessment showing no progression. Subjects who change treatment without evidence of disease progression will be censored at the last assessment showing no progression prior to treatment change.

Time to Next Anti-lymphoma Treatment

Time to next anti-lymphoma treatment is defined as the time from the first dose date of maintenance therapy to the time of first documented administration of new anti-lymphoma therapy. Subjects without new treatment therapy will be censored at the last visit.

Time to Histological Transformation

Time to histological transformation is defined as the time from the first dose date of maintenance therapy to the time of histological transformation as measured based on documentation of histological transformation (as assessed by the investigator). In case of clinical suspicion of transformation, including rapid disease progression, unexpected changes in "B" symptoms or rapidly increasing LDH, a biopsy should be performed. In this clinical trial, histological transformation will be considered disease progression. This endpoint will not be calculated for subjects randomized with transformed Follicular Lymphoma (tFL).

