This Phase 3b multicenter, randomized, open-label study will enroll subjects with relapsed/refractory follicular lymphoma grades 1-3b, transformed follicular lymphoma, marginal zone lymphoma or mantle cell lymphoma. All subjects enrolled will receive 12 cycles of lenalidomide plus rituximab induction therapy.

The study is designed to compare the efficacy and safety of two maintenance regimens following the induction therapy. Subjects who have stable disease (SD), partial response (PR), unconfirmed complete response (CRu) or complete response (CR) at the end of 12 cycles of induction therapy will be randomized to one of two maintenance arms: Arm A (experimental) or Arm B (control). Subjects randomized to Arm A will receive lenalidomide plus rituximab combination maintenance therapy (for 18 cycles) followed by optional lenalidomide single-agent maintenance (to progression). Subjects randomized to Arm B will receive rituximab single-agent maintenance (for 18 cycles).

Subjects will be stratified at time of randomization to the maintenance arm by histology, lines of anti-lymphoma therapy, and age.

The overall study design is described in Figure 1. The study is divided into a Screening Period, a Treatment Period (induction and maintenance), and a Follow-up Period. Approximately 500 subjects are planned to be enrolled.

Upon giving written informed consent, a subject will enter the Screening Period and undergo safety and other assessments to determine eligibility for the study. All Screening assessments must be completed within 28 days prior to the subject initiating induction therapy.

Subjects enter the Induction Treatment Period at the time they complete screening procedures and meet all eligibility criteria. Eligible subjects entering the Induction Treatment Phase will be enrolled using an Interactive Voice Response System (IVRS). The treatments will be given as described in detail in Section 8 and must begin no later than 1 week after enrollment in IVRS to receive induction therapy. Cycle length during induction and maintenance is 28 days.

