4.1.4 Randomization to Maintenance Treatment Period

After 12 cycles of lenalidomide plus rituximab induction therapy, subjects achieving CR/CRu, PR or having SD will be randomized to enter the maintenance period. During the maintenance period, subjects randomized to Arm B will receive rituximab (only) administered for 18 Cycles. Subjects randomized to Arm A will receive lenalidomide plus rituximab treatment for 18 Cycles and then lenalidomide until relapse or progression of disease. Lenalidomide (only) treatment in Arm A will be given per subject and/or physician discretion as described in detail in Section 8 and must begin no later than 1 week after the last cycle of rituximab plus lenalidomide. Subjects randomized under previous protocol (version 16 January 2014) who achieve a response of SD or better at the end of the Induction Treatment Period will remain in their originally assigned arm of maintenance therapy.

All subjects (in both Induction and Maintenance Treatment Periods) receive treatment as described unless they withdraw consent from treatment, experience unacceptable toxicities or have disease progression. Once subjects discontinue or complete treatment, they enter the follow-up period. All enrolled subjects will be followed for disease progression using the schedule described in Table 1. Subjects who progress before the end of planned treatment will enter the Follow-up Period. Determination of disease progression will be based on investigator assessment. All subjects who discontinue the protocol-specified treatment early for any reason without documented evidence of disease progression will also be followed in the Follow-up Period.

All subjects who will be on treatment upon reaching 5 years after the last subject has initiated induction therapy will continue the treatment and will be followed up for safety purposes only.

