10.6.4 Analysis Methods

Time-to-Event Endpoints

For the time-to-event endpoints, the Kaplan-Meier estimates of the survival function will be calculated and graphically presented. The stratified log-rank test will be performed to evaluate treatment efficacy. The experimental arm will be declared superior if the 2-sided p-value from the stratified log-rank test is less than or equal to the desired significance level in favor of the experimental arm. The un-stratified log-rank test will be performed as sensitivity analysis.

Hazard ratio with two-sided 95% confidence interval (CI) will be estimated using the Cox proportional hazards model.

Binary Endpoints

The binary endpoints such as IOR will be summarized in frequency and percentage. The stratified Cochran-Mantel-Haenszel (CMH) test will be performed to evaluate treatment efficacy. The unstratified CMH test will be performed as sensitivity analysis.

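### Section 10.6.2 names no denominator for Improvement of Response, so by default it includes CR/CRu subjects who cannot improve; this lowers the rate and costs some precision, but the comparison stays valid.

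*Combined protocol and SAP*

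**What the plan says.** Entry to maintenance (Section 4.1.4): after induction, "subjects achieving CR/CRu, PR or having SD will be randomized to enter the maintenance period". Complete responders are therefore part of the randomised comparison.

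Analysis set (Section 10.2): "The ITT population is defined as all subjects who are randomized and have received at least one dose of maintenance therapy". Section 10.6 then applies it generally: "All efficacy analyses will be performed on the ITT population". The supportive mITT set also admits CR/CRu.

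Endpoint (Section 10.6.2): "Improvement of response is defined as the proportion of subjects who have improved their tumor response during the maintenance phase". Two transitions count. The first is "the proportion of subjects who are converted from PR at the end of induction period to CR/CRu as best response"; the second is from SD to PR or better. No denominator is named.

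Contrast within Section 10.6.2: other endpoints carry an express restriction. "Duration of response is defined only for subjects who have achieved PR or better after the first dose date of maintenance therapy". DOCR is limited in the same way to subjects who reach CR/CRu, and TTHT is not calculated for subjects randomised with transformed FL.

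Test (Section 10.6.4, which names IOR as an example of a binary endpoint): "The stratified Cochran-Mantel-Haenszel (CMH) test will be performed to evaluate treatment efficacy". The unstratified version is a sensitivity analysis. The randomisation factors are given in the Protocol Summary: "Subjects will be stratified at time of randomization to the maintenance arm by histology, lines of anti-lymphoma therapy, and age". End-of-induction response is not among them.

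**The concern.** A subject who enters maintenance in CR/CRu has no better category to move to. If such subjects stay in the denominator, they count as non-improvers in both arms whatever the treatment does. Two things follow.

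First, the reported percentage is scaled down by the CR/CRu share, so it does not answer how often maintenance deepens a response that could still deepen. It is also hard to compare with another study that has a different share.

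Second, the two arms will differ by chance in that share. The planned strata do not include it, so the stratified test does not remove that noise. At stake is the readability and power of one secondary endpoint.

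**Working it through.** **Figures in the plan.** No rate, effect size or power is given for IOR, so there is no IOR figure to reproduce. As a check on the reading of the design inputs only, the PFS figures in Section 10.3 do reproduce. The original hazard ratio is 0.533/0.8 = 0.667. Schoenfeld's formula at one-sided 0.025 then gives 191 events for 80% power (191 stated), and at 114 events it gives 58.1% power (57.9% stated).

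**Inputs.**
- Subjects per arm: 314/2 = 157, from the projection in Section 10.3. The number actually randomised is not given.
- CR/CRu share f: not given. Two cited lenalidomide-rituximab studies give a rough guide. In relapsed FL (Section 1.6.1), 32% CR out of 75% response is 32/75 = 43% of responders. In MCL (Section 1.6.3), 36/57 = 63%. Subjects with SD are also randomised, which lowers the share. Range used: 30% to 60%.
- Improvement rates among SD/PR subjects: not given. Three assumed pairs: 40% v 25%, 20% v 10%, 50% v 30%.
- Significance level: one-sided 0.025, assumed for IOR because the plan states it only for PFS.
- Stratum shares: assumed. Histology 80/10/10, lines of therapy 60/40, age 45/55, giving 3 × 2 × 2 = 12 strata, with the same improvement rates in every stratum.

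**Step 1: the rate.** ITT rate = (1−f) × rate among improvable subjects. With f = 50%, 40% v 25% becomes 20.0% v 12.5%. The risk ratio is 40/25 = 20.0/12.5 = 1.6 either way. The risk difference falls from 15 to 7.5 points.

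**Step 2: the test statistic, unstratified.** Let d be the difference and p the average rate among improvable subjects, with n per arm.
- Restricted: z = d / √[2p(1−p) / (n(1−f))].
- All ITT: z = (1−f)d / √[2p(1−f)(1−p(1−f)) / n].
- Ratio of all-ITT to restricted: √[(1−p) / (1−p(1−f))], below 1 whenever f > 0.
- p = 0.15, f = 30%: √(0.85/0.895) = 0.975.
- p = 0.325, f = 50%: √(0.675/0.8375) = 0.898.
- p = 0.40, f = 60%: √(0.60/0.84) = 0.845.

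The loss therefore grows with both f and p.

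**Step 3: chance imbalance in f.** At f = 43%, the standard error of the between-arm difference in the CR/CRu share is √(2 × 0.43 × 0.57 / 157) = 5.6 points.

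**Step 4: power of the planned test.** The 12-stratum CMH test was simulated with 40,000 replicates per row; Monte Carlo error is about 0.25 points on each power, and losses are taken before rounding.

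| Rates among improvable | f | Power, all ITT | Power, SD/PR only | Loss (points) |
|---|---|---|---|---|
| 40% v 25% | 30% | 58.9% | 64.2% | 5.3 |
| | 40% | 50.8% | 56.9% | 6.1 |
| | 50% | 43.2% | 49.4% | 6.2 |
| | 60% | 34.5% | 40.5% | 5.9 |
| 20% v 10% | 30% | 51.4% | 52.8% | 1.4 |
| | 40% | 45.0% | 46.6% | 1.6 |
| | 50% | 38.1% | 39.6% | 1.5 |
| | 60% | 30.9% | 31.9% | 1.0 |
| 50% v 30% | 30% | 77.8% | 84.4% | 6.6 |
| | 40% | 68.8% | 77.9% | 9.1 |
| | 50% | 58.5% | 69.8% | 11.3 |
| | 60% | 47.8% | 59.3% | 11.5 |

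Repeat runs move the losses by a few tenths of a point. With equal rates in the two arms (30% v 30%), both versions reject in about 2.5% of replicates.

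**The case against.** **The denominator is inferred.** Section 10.6.2 never says all ITT, and its wording names SD and PR starters. That is correct, and the defect is best described as an unnamed denominator. But Section 10.6 covers every efficacy analysis, and the plan restricts DOR, DOCR and TTHT in words when it means to. A programmer following the text would use all ITT.

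**The all-ITT proportion is a legitimate quantity.** This also stands. It answers a different question, how many of those randomised improved, and the test on it is valid. It is low only when read as the rate among subjects able to improve.

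**The size is assumed.** This stands too. No single loss in power can be attributed to the plan.

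**The restriction is not purely a baseline one.** Sections 4.1.4, 8.2 and 8.3 keep subjects randomised under the 16 January 2014 version in their original arm, and that version randomised before induction. For them, end-of-induction response comes after randomisation and is judged by investigators in an open-label study. Both arms receive the same induction, which limits the risk, but the number of such subjects is not given. In addition, CR/CRu in gastric MZL needs biopsies over up to 3 months (Sections 6.1.6 and 6.3), so the label may be settled after maintenance starts. The IOR definition already needs that label under either denominator. These points justify keeping the all-ITT figure in view, not leaving the denominator unnamed.

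**Conclusion.** The point holds as a gap in definition with a modest cost. If the plan is followed as written, IOR is diluted by the factor (1−f), and the stratified CMH test loses power in every scenario examined: about 5 to 7 points at 40% v 25%, 1 to 2 at 20% v 10%, and 6 to 12 at 50% v 30%. These figures rest on the assumed f, rates, stratum shares and 157 per arm.

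Three stronger readings are not supported:
- A reader might infer a biased or invalid comparison. Type I error and the expected risk ratio are unchanged.
- A reader might infer that the rate mainly reflects how many subjects entered in CR. It is scaled by that share; at f = 30% it is still 70% of the rate among improvable subjects.
- A reader might infer a fixed loss of 6 to 9 points. That comes from an unstratified test at 40% v 25% only, and Section 10.6.4 makes the unstratified test a sensitivity analysis.

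IOR is one of eight secondary efficacy endpoints and carries no power claim. The primary PFS analysis is not affected.

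**What to change.** In Section 10.6.2, define the main IOR analysis on ITT subjects with SD or PR at the end of induction, and report the all-ITT proportion beside it. For the test alone, an equivalent is to keep all ITT subjects and add end-of-induction response (CR/CRu versus SD/PR) as a CMH stratifying factor. The CR/CRu strata then have no events in either arm and contribute nothing.

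Add two sentences: one stating which assessment fixes end-of-induction status, including gastric MZL with biopsies pending; the other noting that this status is post-randomisation for subjects randomised under the 16 January 2014 version, with a sensitivity analysis that leaves them out.

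The cost is a short text change and one extra table. No new data are needed, because the endpoint already requires end-of-induction response. The choice should be recorded before the final analysis, since a denominator chosen after results are seen in an open-label study would be open to challenge.
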